Seizure counts, cognitive, developmental level, and behavioral assessments will be summarized by treatment group and age group. The incidence of suicide-related thoughts and behaviors as determined by the C-SSRS will be summarized by treatment group and age group.

For the cognitive assessments, standardized change from baseline scores will be calculated by computing the change for each postdose assessment score from the baseline assessment score, relative to the expected within-subject standard deviations for each Cogstate task. For the tasks for which lower scores indicate improvement (eg, Detection Test and Identification Test), the score will be multiplied by (-1), so that negative standardized scores represent a decline in cognitive performance consistently across all tasks.

A meaningful decline in cognition has been defined as a standardized change of less than -1.65 from the baseline assessment. These calculations will indicate meaningful decline at the subject level. For each individual score assessment, standardized change scores that meet the definition of a meaningful decline will be identified using a binary flag, where 1 represents a meaningful decline from baseline and 0 otherwise.

Group-based summary data (frequency distribution of the binary flags) will also be presented by computing the proportion of subjects who meet the criteria for meaningful decline at each postdose assessment.

In addition to the above endpoints, other safety-related endpoints may be included in the analyses and summarized if deemed necessary.

Adverse Events

The verbatim terms used in the CRF by investigators to identify adverse events will be coded using the Medical Dictionary for Regulatory Activities (MedDRA). All reported adverse events with onset during the treatment phase (ie, treatment-emergent adverse events, and adverse events that have worsened since baseline) will be included in the analysis. For each adverse event, the percentage of subjects who experience at least 1 occurrence of the given event will be summarized by treatment group and by age group.

Summaries, listings, datasets, or subject narratives may be provided, as appropriate, for those subjects who die, who discontinue treatment due to an adverse event, or who experience a severe or a serious adverse event.

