2.5. Randomization and Blinding

Procedures for Randomization and Stratification

Subjects will be randomly assigned to 1 of 2 treatment groups based on a computer-generated randomization schedule prepared before the study by or under the supervision of the sponsor. The randomization will be balanced using randomly permuted blocks and will be stratified by country and age group (2 to 5 years of age, 6 to 9 years of age, 10 to 12 years of age, and 13 to 15 years of age). The enrollment will be monitored throughout the study to ensure that subjects are enrolled for each integer year in each treatment group.

Based on this information, the interactive web-based response system (IWRS) will assign a unique treatment code, which will dictate the treatment assignment and matching study drug kit for the subject. As subjects are randomly assigned to treatment, the IWRS will assign a study drug kit to be dispensed at that visit. New study drug kits will be assigned each time the IWRS is accessed for dispensing additional study drug.

Blinding

As this is an open-label study, blinding procedures are not applicable for treatment assignment.

To minimize any bias in measurement, after randomization 3 of the safety assessments will be obtained in a blinded fashion, including the DEXA scan, renal ultrasound, and height.

Renal ultrasound will be read/interpreted centrally (local reading at the screening visit is acceptable to determine eligibility for study enrollment). Both the technicians administering the renal ultrasound scans and the local and central readers will be blinded to the study treatment group.

All DEXA scans will be centrally analyzed (the baseline scans will be read locally to determine eligibility for the study). Both the technicians administering the DEXA scans and the central reader will be blinded to the treatment group.

Height will be measured by a trained individual who is blinded (unaware of the treatment).

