5. SUBJECT INFORMATION

5.1. Demographics and Baseline Characteristics

Subject demographics and baseline disease characteristics will be listed and summarized for the randomized analysis set by treatment group. Descriptive statistics (mean, standard deviation, median, minimum, and maximum) will be presented for age, height, weight, body mass index (BMI), and years since diagnosis of epilepsy. Frequency counts and percentages will be presented for categorical variables sex, age group (2-5 years, 6-9 years, 10-12 years, 13-15 years), ethnicity, race, geographic region, seizure types present within the last 2 years, seizure occurred within the last 2 years beyond 3 or 5 month, seizure occurred in last 3 or 5 months and any AED drug/therapy at study entry and bicarbonate categories. Bicarbonate values are categorized as low (<20 mEq/L at screening) and non-low bicarbonate values (\geq 20 mEq/L at screening).

Age in years will be used from eCRF. In case of missing eCRF for age, 15th of the month will be used as day. Missing day and month at date of birth will be imputed by June 30. Years since diagnosis of epilepsy will be calculated based on year of Day 1 minus year of diagnosis (if both in the same year it will be 0).

- Age calculation:
 - For Height and Weight Z-Scores, it is given in CDC guidance document, age is in month with one decimal.
 - For demographics, it is floor (ICF date minus birth date)/365.25), age is in full years.
 - For Vineland it is floor ((intck ('month', birth date, visit date)-(day (visit date)<day(birth date))))), age is in full month.
 - For CBCL it is floor (visit date minus birth date)/365.25), age is in full years.
 - For Cogstate it is floor (visit date minus birth date)/365.25), age is in full years.
 - For vital signs it is floor (visit date minus birth date)/365.25), age is in full years.
 - For labs it is floor (visit date minus birth date)/365.25), age is in full years.
 - Age for determination of max daily dose for Topiramate or Levetiracetam it is floor (date of dosing minus birth date)/365.25), age is in full years.
- BMI is calculated as weight (kg) / height (m)².

Geographic region will be summarized as North America, South America, Europe and Asia Pacific.

- North America: US, Canada
- South America: Argentina, Mexico
- Europe: Belgium, France, Germany, Hungary, Italy, Poland, Russian Federation, Austria, South Africa, UK
- Asia Pacific: Australia, Taiwan, Philippines

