7. SAFETY

The safety variables to be summarized include kidney stones, height, weight, BMD and bone mineral content (BMC), biochemical markers of bone mineralization, bone age XR, seizure counts, cognitive, developmental, and behavioral assessments, treatment-emergent AEs, Columbia-Suicide Severity Rating Scale (C-SSRS), cognitive, developmental and behavioral assessments (COGSTATE computerized battery and NEPSY Language scale; Vineland Adaptive Behavioral Scale, Child Behavior Checklist (CBCL)), clinical laboratory tests (hematology, chemistry, urinalysis, and 24-hour urine collection), vital signs and physical exam. Safety variables are to be tabulated by descriptive statistics (n, mean, median, SD, minimum, and maximum; or n and percent). No formal statistical testing is planned.

For markedly abnormal labs and vital signs, age will be calculated at each visit to determine the criteria. Similarly, Vineland, CBCL and Cogstate will be calculated by age at each visit.

Z-scores for weight and height will be calculated using the SAS programs provided by the Centers for Disease Control (CDC) for the calculation of the 2000 CDC growth charts. Z-scores for the BMD and BMC will be provided by the central DEXA reading center (Bioclinica).

Z-scores for the DEXA scans will be calculated locally at baseline only to determine eligibility for the study, and centrally for all statistical analyses. The Z-score calculation will take the DEXA machine and the subject's age, sex, height, and ethnicity into consideration. The reference databases for calculating the Z-scores are provided in the DEXA Manual for this study (please see the imaging charter of attachment 1 for more details).

Longitudinal endpoints will be analyzed using a mixed-model repeated measures (MMRM) analysis. An MMRM analysis is included as sensitivity analysis to explore longitudinal safety data and will be analyzed in the following order.

1. The model includes treatment group, study center, age group (4 age groups), visit, treatment-by-visit interaction, baseline measure, and baseline-by-visit interaction with the unstructured covariance matrix.
2. If this model experiences convergence issues, then the same model with compound symmetric matrix followed by AR1 will be explored instead of unstructured.

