7.8. Cognitive, Developmental, and Behavioral Assessments

Cognitive Assessments

For the cognitive assessments (Detection Test, Identification Test, One Card Learning Test, One Back Test, and Groton Maze Learning Test) the standardized observed scores and change from baseline in standardized scores will be listed and summarized by visit using descriptive statistics. The standardized scores will be calculated by setting the observed raw score in relation to the expected within-subject standard deviations for each Cogstate task (see table 1-5 of [Appendix 1](#) for normative data). For the tasks which lower scores indicate improvement (e.g., Detection Test and Identification Test), the score will be multiplied by (-1), so that a negative change in standardized scores represent a decline in cognitive performance consistently across all tasks.

A meaningful decline in cognition has been defined as a change in standardized score of less than -1.65 from the baseline standardized score. These calculations will indicate meaningful decline at the subject level. Each individual change in standardized scores that meet the definition of a meaningful decline will be identified using a binary flag, where 1 represents a meaningful decline from baseline and 0 otherwise. The number and percentage of subjects with a meaningful decline in cognition will be listed and summarized by visit.

Cognitive assessments will be provided to subjects of 4 years and older. Cognitive data collected after a subject turn 16 will not be included in the analysis.

For example, if a 10-year-old female subject has an observed raw score at baseline of 1.2 for the detection test, then the standardized score will be $1.2/0.0882*(-1)=-13.605$. For a post baseline visit the subject had an observed raw score of 1.0, which is a standardized score of -11.338. The

change from baseline would be 2.267. The lower score at post baseline indicates an improvement in Detection Test which is reflected by the positive change (see table 1 of [Appendix 1](#)).

Developmental Assessments

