10. APPENDICES

Appendix 1: Cogstate Pediatric Normative Data**Table 1: CogState Pediatric Normative Data for the Detection Task.**

Age (years)	Males			Females		
	N	M	SD	N	M	SD
2	–	–	–	–	–	–
3	–	–	–	1	2.9041	–
4	2	2.8775	0.0534	3	2.8581	0.1732
5	4	2.7714	0.1001	10	2.7341	0.0871
6	5	2.6002	0.0717	11	2.8240	0.1660
7	6	2.6733	0.1357	9	2.7294	0.0622
8	4	2.6115	0.1769	6	2.8202	0.1598
9	4	2.5632	0.1146	3	2.5398	0.0714
10	1224	2.5631	0.0870	210	2.5882	0.0882
11	1499	2.5388	0.0826	506	2.5641	0.0899
12	1882	2.5290	0.0842	816	2.5447	0.0831
13	2322	2.5177	0.0851	1076	2.5255	0.0767
14	6551	2.5121	0.0853	3315	2.5252	0.0826
15	6399	2.5086	0.0810	3347	2.5213	0.0821

Note: The primary outcome variable for the Detection task is Reaction Time (Log10 transformation).

Table 2: CogState Pediatric Normative Data for the Identification Task.

Age (years)	Males			Females		
	N	M	SD	N	M	SD
2	–	–	–	–	–	–
3	–	–	–	1	3.1028	–
4	2	3.0312	0.0142	3	3.1244	0.0795
5	4	2.9061	0.0266	10	2.9546	0.1075
6	5	2.9199	0.0931	11	2.9938	0.1276
7	6	2.9238	0.1067	9	2.9310	0.0849
8	4	2.8885	0.1575	6	2.9726	0.1053
9	4	2.7421	0.0453	3	2.7632	0.0634
10	1198	2.7637	0.0759	203	2.7796	0.0735
11	1456	2.7323	0.0739	499	2.7453	0.0727
12	1823	2.7163	0.0712	811	2.7186	0.0726
13	2279	2.7007	0.0725	1073	2.6973	0.0711
14	6470	2.6889	0.0731	3300	2.6903	0.0719
15	6324	2.6809	0.0700	3335	2.6800	0.0717

Note: The primary outcome variable for the Identification task is Reaction Time (Log10 transformation).

Table 3: CogState Pediatric Normative Data for the One Card Learning Task.

Age (years)	Males			Females		
	N	M	SD	N	M	SD
6	5	1.0120	0.1845	11	1.0029	0.1441
7	6	0.9715	0.1175	9	0.9300	0.1616
8	4	1.1346	0.0765	6	0.9942	0.1889
9	4	1.0406	0.0376	3	0.9863	0.1306
10	1147	0.9639	0.0880	201	0.9636	0.0910
11	1449	0.9646	0.0889	485	0.9650	0.0892
12	1837	0.9719	0.0889	807	0.9692	0.0875
13	2249	0.9722	0.0858	1053	0.9767	0.0874
14	6435	0.9715	0.0870	3347	0.9679	0.0858
15	6559	0.9739	0.0868	3434	0.9718	0.0854

Note: The primary outcome variable for the One Card Learning task is Accuracy (arcsine square-root transformation).

Table 4: CogState Pediatric Normative Data for the One Back Task.

Age (years)	Males			Females		
	N	M	SD	N	M	SD
6	5	3.0924	0.0965	11	3.1386	0.1728
7	6	3.0799	0.0686	9	3.0789	0.0926
8	4	2.9574	0.0691	6	3.1290	0.1488
9	4	2.9524	0.0589	3	2.9646	0.1824
10	1278	2.9597	0.0984	218	2.9840	0.0990
11	1576	2.9225	0.0958	548	2.9405	0.0962

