12	1973	2.8977	0.0962	879	2.9139	0.0972
13	2437	2.8824	0.0945	1130	2.8931	0.0938
14	7000	2.8673	0.0935	3604	2.8851	0.0930
15	7061	2.8547	0.0926	3663	2.8716	0.0952

Note: The primary outcome variable for the One Back task is Reaction Time (Log10 transformation).

Table 5: CogState Pediatric Normative Data for the Groton Maze Learning Test.

Age (years)	Males			Females		
	N	M	SD	N	M	SD
6	–	–	–	2	63.5000	16.2635
7	1	102.0000	–	–	–	–
8	–	–	–	1	68.0000	–
9	3	64.6667	24.0069	1	27.0000	–
10	20	73.8500	31.0251	6	67.3333	25.5943
11	14	67.6429	22.4828	12	64.1667	14.9595
12	20	62.9500	18.9667	6	61.0000	14.0855
13	10	53.2000	19.0660	11	65.0000	15.7861
14	5	61.6000	16.7422	2	46.0000	19.7990
15	–	–	–	1	39.0000	–

Note: The primary outcome variable for the Groton Maze Learning Test is Total Errors.

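### SAP 7.8 divides each uncentred Cogstate raw score by the norm SD for age at that visit, so a birthday alone can create or hide a meaningful decline, mainly at ages 4-9

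*SAP*

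**What the plan says.** SAP 7.8 defines the score: "The standardized scores will be calculated by setting the observed raw score in relation to the expected within-subject standard deviations for each Cogstate task". The sign is reversed for tasks where a lower score is better. The baseline standardised score is subtracted from the post-baseline one, and a change below -1.65 is flagged as a meaningful decline.

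The age used to look up the SD is the age at the visit. SAP 7 states that "Vineland, CBCL and Cogstate will be calculated by age at each visit", and SAP 5.1 adds "For Cogstate it is floor (visit date minus birth date)/365.25), age is in full years". Nothing in the SAP holds the baseline SD fixed for later visits. The only age limit is "Cognitive data collected after a subject turn 16 will not be included in the analysis".

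Protocol 11.4 has a different order of operations: "computing the change for each postdose assessment score from the baseline assessment score, relative to the expected within-subject standard deviations for each Cogstate task". There the raw change is formed first and then scaled. The protocol does not say which age's SD applies, or that one SD is kept per child.

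**The concern.** Dividing an uncentred score by an SD gives a large number. Across Appendix 1 Tables 1-4, norm mean over norm SD runs from about 5 (One Card Learning, girls aged 8: 0.9942/0.1889 = 5.3) to 213 (Identification, boys aged 4: 3.0312/0.0142 = 213.5). When two such numbers with different divisors are subtracted, even a modest difference in SD can exceed the 1.65 cut-off with no change in performance.

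The SDs at ages 4-9 come from 2 to 11 children per sex-by-age cell and move erratically from year to year. At ages 10-15 they come from about 200 to 7,000 children per cell and are stable.

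Cognitive disorders are a listed adverse event of interest for topiramate, and this flag is the subject-level result of the Cogstate tests. The summaries of mean change in standardised score carry the same shifts, and SAP 3.4 also summarises data by age group, so the 6-to-9 table would be heavily affected.

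**Working it through.** **The SAP's own example.** Detection, girl aged 10, SD 0.0882 (Appendix 1 Table 1, "CogState Pediatric Normative Data for the Detection Task"): -1.2/0.0882 = -13.605 and -1.0/0.0882 = -11.338, so the change is 2.267. This reproduces. It uses the same SD at both visits, so it cannot show the effect of a birthday.

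**Effect of a birthday alone.** For each sex, task and step from age a to a+1, with the raw score held at the age-a norm mean M:

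shift = sign × (M_a/SD_(a+1) − M_a/SD_a)

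The sign is −1 for reaction-time tasks and +1 for One Card Learning. Examples:

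- Detection, boy 8 to 9: 2.6115/0.1769 = 14.76; 2.6115/0.1146 = 22.79; shift −8.03, a false decline.
- Detection, girl 6 to 7: 2.8240/0.1660 = 17.01; 2.8240/0.0622 = 45.40; shift −28.39, a false decline.
- Identification, boy 4 to 5 (cells of 2 and 4 boys): 3.0312/0.0142 = 213.46; 3.0312/0.0266 = 113.95; shift +99.51, which would mask a decline.
- Detection, girl 12 to 13: 2.5447/0.0831 = 30.62; 2.5447/0.0767 = 33.18; shift −2.56, a false decline even with large norm cells.

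All steps in Tables 1-4 (Detection, Identification, One Card Learning, One Back), not weighted by enrolment:

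| Starting age | Steps | Below −1.65 | Above +1.65 | Median absolute shift |
|---|---|---|---|---|
| 4-9 | 40 | 14 | 23 | 11.4 |
| 10-14 | 40 | 2 | 1 | 0.36 |
| All | 80 | 16 | 24 | |

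The three at ages 10-14 are all Detection in girls: 11 to 12 (−2.33), 12 to 13 (−2.56) and 13 to 14 (+2.35). Three more steps in that range lie between −1.56 and −1.63.

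The result does not depend on holding the raw score still. If the child moves from the age-a norm mean to the age-(a+1) norm mean, the SAP rule puts 16 steps below −1.65 and 25 above +1.65. Raw change over the baseline-age SD puts 1 and 7 there.

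**Flag rates.** Assume raw change is normal with SD k times the baseline-age norm SD, with k = 1 and a range of 0.5 to 1.41. With no true change, the SAP-rule flag rate at a birthday crossing is the mean over cells of Φ((−1.65 − shift)/(k × SD_a/SD_(a+1))). With one fixed SD it is Φ(−1.65/k).

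| At a birthday crossing | Fixed SD | SAP rule, ages 4-9 | SAP rule, ages 10-14 |
|---|---|---|---|
| Flagged, no true change | 4.9% (0.05-12.1%) | 35.9% (35.1-36.5%) | 14.8% (9.9-20.0%) |
| Flagged, true 2-SD decline (k = 1) | 63.7% | 41.7% | 67.5% |
| Gap in percentage points | 59 (48-76) | 6 (5-6) | 53 (44-64) |

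**How often it happens.** With evenly spread birthdays, 179/365.25 = 49% of children cross one by Day 180 and 359/365.25 = 98.3% by Day 360 among those followed that long. If all of the planned 29% dropouts leave first, the latter is 98.3% × 0.71 = 69.8%.

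**Groton Maze.** Table 5 ("CogState Pediatric Normative Data for the Groton Maze Learning Test") has no SD in 8 of its 20 sex-by-age cells (boys 6, 7, 8 and 15; girls 7, 8, 9 and 15), so no score can be computed there. It is left out of the counts above. Of its 9 computable steps, 1 crosses the cut-off (girl 10 to 11, −1.87).

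**The case against.** The strongest reply is that the fixed-SD comparator is idealised. It assumes that raw change varies in proportion to the same norm SD used as the divisor, so 4.9% holds in every cell by construction. Suppose instead that the true variability is smooth across ages 4-9, taken as either the age-10 SD or the root-mean-square of the age 4-9 SDs for the task. Dividing by the baseline-age SD then gives false-flag rates averaging 6-10%, with single cells from about 0.03-0.3% up to 38-40% (Identification, boys aged 4, SD 0.0142 from 2 children), and a gap of 42-55 points. This stands as a caution: small norm cells are a second cause of error, and freezing the age does not cure it. It does not rescue the SAP rule, which under the same alternatives still flags about 35-36% with a gap of 5-6 points.

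Second, the 6-point gap applies only once a birthday has been crossed. At Day 180 the blended gap at ages 4-9 is about 0.49 × 6 + 0.51 × 59 = 33 points. It approaches 6 only near Month 12 in children followed that long. That is correct.

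Third, the impact is bounded. Cogstate is not a key endpoint, no formal testing is planned, cognitive adverse events are summarised separately, enrolment stopped early (SAP 1), and the number of children aged 4-9 is unknown. Randomisation is "stratified by country and age group", so both arms should be affected alike. All of this is true. It limits the severity and does not make the derivation right.

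**Conclusion.** The concern holds. The rule as written gives wrong results; it is not merely short of detail. At ages 4-9 a birthday moves the score past 1.65 in 37 of 40 steps, and after a birthday the flag barely separates a true 2-SD decline from no change (6 points, against 59 with a fixed SD). At ages 10-14 the effect is small (3 of 40 steps; 53 points).

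The step counts rest only on Appendix 1 and on the raw score being at the norm mean. The flag rates rest also on the normal-change assumption and weight cells equally, not children. The expected consequence is misclassified decline rates in both arms and dilution of any real difference, not bias toward one drug. It should be fixed, but it does not threaten the key endpoints.

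**What to change.** Restore the order in Protocol 11.4: take post-baseline minus baseline raw score, reverse the sign where lower is better, divide by a single SD per child and task used at all visits, and apply −1.65. An unchanged raw score then gives exactly 0, and the SAP's worked change of 2.267 is unaffected. Taking the SD at baseline age and sex is one workable choice; it is a proposal here and is not stated in the protocol.

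At ages 4-9, and in the empty Groton Maze cells, use a pooled SD or the vendor's within-subject SD. The latter is not in the documents and would have to be obtained. Centring each score on the visit-age mean is not enough: for an unchanged raw score, Identification in boys 8 to 9 would still shift by (2.7421 − 2.8885)/0.0453 = −3.23.

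Take Cogstate out of the age-at-visit rule in SAP 7 and 5.1. The exclusion of data after a child turns 16 can be applied directly from birth and visit dates.

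The cost is SAP wording and one derivation, with no new trial data. The summaries of standardised observed scores would change or be dropped, and the pooled or vendor SD has to be agreed.

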The Cogstate pediatric normative database consists of cognitive tests from over 55,000 healthy children. The majority of the data are from select test scales (One Card Learning Test, One Back Test, Detection Test, Identification Test) in 10- to 18-year-old children, but there are data on the Groton Maze Learning Test in younger children. Furthermore, the Cogstate tests have been shown to have demonstrated utility in pediatric clinical studies in oncology, and in the treatment of disorders such as attention-deficit/hyperactivity disorder, HIV, neurodevelopmental disorders, and sickle cell disease.

The semantic item “Animals” from the Word Generation subtest of the NEPSY-II (A Developmental NEuroPSYchological Assessment) will be included in this study. This test measures verbal productivity through the ability to generate words within specific categories and is a commonly used and standardized measure of language and executive functioning in children and adolescents. This will be administered by study site personnel who are trained according to a study-specific rater training plan. The test will be scored by the site rater and the data will be transferred to Cogstate.

Developmental Assessments in Subjects 2 to 5 Years of Age

The Vineland Adaptive Behavior Scale will be administered for subjects 2 to 5 years of age, to assess developmental level and adaptive functioning. For very young children, the behaviors assessed are closely correlated with developmental milestones.

The Vineland Adaptive Behavior Scale, version II focuses on behaviors needed to operate in an age-appropriate manner in the individual’s environment. It is age-specific and provides an assessment of function in the domains of communication, daily living, socialization, and motor skills, as well as a composite scale. The Vineland scores have a mean of 100 and a standard deviation of 15, based on a normative population sample.^{6,36}

The interview will be completed by the parent/guardian and will be scored by a trained rater at screening, at Month 3, Month 6, and Month 12/early withdrawal.

Behavioral Assessments

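### The Cogstate decline flag is defined in within-subject SDs, but the SAP divides by age- and sex-specific norm-sample SDs, so the -1.65 cutoff does not have its stated meaning

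*SAP*

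**What the plan says.** Protocol 11.4 takes each postdose change from baseline and scales it "relative to the expected within-subject standard deviations for each Cogstate task". The cutoff follows: "A meaningful decline in cognition has been defined as a standardized change of less than -1.65 from the baseline assessment".

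SAP 7.8 keeps the idea but changes the order. It standardizes each raw score "in relation to the expected within-subject standard deviations for each Cogstate task", refers to Tables 1 to 5 of Appendix 1 for the values, and then takes the difference. The flag is "a change in standardized score of less than -1.65 from the baseline standardized score".

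The first of those tables is headed "CogState Pediatric Normative Data for the Detection Task". It lists N, M and SD by year of age and sex, as do the other four. The worked example in SAP 7.8, a girl aged 10 on Detection, computes "1.2/0.0882*(-1)=-13.605".

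On age, SAP 7 says: "Similarly, Vineland, CBCL and Cogstate will be calculated by age at each visit". SAP 5.1 gives the formula, full years at the visit date.

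**The concern.** A within-subject SD measures how much one child's score varies between sittings. A normative SD by age and sex measures how much different children vary. The cutoff of -1.65 is set in units of the first, and the SAP supplies the second. The reported percentage with meaningful decline would then not answer the question its label poses.

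Cognitive disorders are a named topiramate event of interest (Protocol 11.4, SAP 7.9), and this flag is the subject-level decline summary for Cogstate. A reader of the study report would take it at face value.

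**Working it through.** **The plan's own figure.** Score = -raw/SD with SD = 0.0882 (Appendix 1 Table 1, girls aged 10, N = 210). Baseline: -1.2/0.0882 = -13.605. Follow-up: -1.0/0.0882 = -11.338. Change: 2.267 from the rounded scores. The example reproduces, so the divisor in use is the table SD.

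**What kind of SD it is.** Appendix 1 does not label it. Protocol 9.3 describes the source: "The Cogstate pediatric normative database consists of cognitive tests from over 55,000 healthy children". Cells with N = 1 have no SD. The two Groton Maze cells with N = 2 match two whole-number error counts:
- girls aged 6: 16.2635 × √2 = 23.0, mean 63.5, so scores of 52 and 75;
- girls aged 14: 19.7990 × √2 = 28.0, mean 46, so scores of 32 and 60.

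This is a cross-sectional SD over N children. Neither document contains a retest figure.

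**Effect with one fixed divisor.** Let r be the test-retest correlation (assumed; not in the documents). Assume normal errors, no learning effect, and the same population for norms and trial. Then:
- single-score within-subject SD (WSD) = norm SD × √(1-r);
- SD of a change = norm SD × √(2(1-r));
- cutoff in WSD units = 1.65/√(1-r);
- P(flag | true decline of 2 WSD) = Φ((-1.65 + 2√(1-r))/√(2(1-r)));
- P(flag | no change) = Φ(-1.65/√(2(1-r))).

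| r | Cutoff in WSD | Flagged, true 2-WSD decline | Flagged, no change | Norm SD ÷ SD of change |
|---|---|---|---|---|
| 0.3 | 1.97 | 51% | 8.2% | 0.85 |
| 0.5 | 2.33 | 41% | 4.9% | 1.00 |
| 0.6 | 2.61 | 33% | 3.3% | 1.12 |
| 0.7 | 3.01 | 24% | 1.7% | 1.29 |
| 0.8 | 3.69 | 12% | 0.5% | 1.58 |
| 0.9 | 5.22 | 1% | 0.01% | 2.24 |

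Benchmarks:
- If the intended divisor is the WSD: Φ((-1.65 + 2)/√2) = 60% flagged for the 2-WSD decline, and Φ(-1.65/√2) = 12.2% with no change.
- If it is the SD of a change: Φ(2/√2 - 1.65) = 41%, and Φ(-1.65) = 4.9%.

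For girls aged 10 on Detection the cutoff is 1.65 × 0.0882 = 0.1455 log10 units. Since 10^0.1455 ≈ 1.40, that is about 40% slower.

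**Effect of age at each visit.** The protocol's form, change divided by one SD, equals the SAP's difference of two standardized scores only if the divisor is the same at both visits. The SAP score is raw/SD with no norm mean subtracted, so a new divisor at a birthday moves the score even when performance does not. Detection, raw score held at the norm mean for the starting age:
- girls 11 to 12: -2.5641/0.0831 + 2.5641/0.0899 = -2.33, a false decline;
- girls 12 to 13: -2.5447/0.0767 + 2.5447/0.0831 = -2.56, a false decline;
- girls 13 to 14: -2.5255/0.0826 + 2.5255/0.0767 = +2.35, which would offset a real decline.

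There are 22 one-year steps from age 4 to 15 over both sexes. An unchanged score gives a change below -1.65 in 8 Detection and 3 Identification steps, and above +1.65 in 7 and 9. Many of these steps involve cells with N of 2 to 11, but the three shown do not (N = 506 to 3315). Day 1 to Day 360 is 359/365.25 = 98% of a year, so nearly every child passes a birthday by Month 12.

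**Cells that cannot be used or are fragile.** Groton Maze is given at ages 6 to 15, but Table 5 has no SD for boys aged 6, 7, 8 and 15 or girls aged 7, 8, 9 and 15: 8 of 20 cells. Identification boys aged 4 have N = 2 and SD 0.0142, a cutoff of 0.023 log10 units against 0.125 for boys aged 10.

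**The case against.** A reader might infer that the cutoff is simply too wide, that every standardized change is shrunk, and that a topiramate effect on cognition is therefore hidden. The documents do not support that much.

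- Neither r nor a within-subject SD is given, so the percentages are conditional on an assumption.
- The texts do not say whether the SD is for a single score or for a change. If it is for a change, the norm SD is the smaller of the two below r = 0.5, and the cutoff is then too narrow.
- Under the age-at-visit rule the errors go both ways, and in very small cells such as Identification boys aged 4 the cutoff can be too narrow. So it cannot be said that flag counts would rise after correction.
- The same rule applies in both arms, no formal testing is planned (SAP 7), and continuous changes and cognitive adverse events are also summarized.

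All of this stands as a limit on direction and size. It does not remove the mismatch between the definition and the divisor. The continuous standardized changes are no full safeguard either, since they use the same divisors and shift at the same birthdays. The worked example applies one SD at both visits, which may be the intention, but it does not say whether the girl has turned 11, and SAP 5.1 and 7 say otherwise.

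**Conclusion.** Wrong as written. The flag is defined in within-subject SDs and computed with norm-sample SDs; the SAP's own example shows it. That the Appendix 1 SDs are cross-sectional is inferred from the layout and the N = 1 and N = 2 cells.

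With one fixed divisor, the norm SD is at least as large as a single-score within-subject SD in the same population, so under-flagging is likely: 33% to 1% for r from 0.6 to 0.9, against 60%, or 41% if a change SD is meant. The true size is unknown. Separately, and without any assumption about r, age-at-visit divisors can create or mask declines, and the flag cannot be computed from 8 of 20 Groton Maze cells. These are descriptive safety summaries; the key endpoints and the sample size are not affected.

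**What to change.** In SAP 7.8, replace the Appendix 1 divisor by one within-subject (test-retest) SD per task. State its source, say whether it refers to a single score or a change, and use the same value at baseline and every follow-up visit. Exempt the Cogstate divisor from the age-at-visit rule in SAP 5.1 and 7. Keep Appendix 1 only to describe baseline level against norms.

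The documents do not contain such an SD, so it has to be obtained. The trial's own practice sessions would be a weak source: learning effects, an interval of at most 35 days, and no statement that the scores are kept for analysis.

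If none can be obtained, fix each child's divisor at the baseline value and relabel the flag as based on norm SDs. That removes the birthday shifts but not the empty or very small cells, so children without a usable SD should be counted as not evaluable.

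The cost is SAP wording and five constants, one per task. Flag counts will change in both arms, in a direction not known in advance.
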